### 1. Abstract

There is a substantial body of work regarding the written anesthesia consent form. As a result, the written anesthesia consent form has become a standard requirement throughout the United States of America. However, there has been little examination of verbal aspects of anesthesia consent and of the value of the preoperative anesthesia discussion that should take place prior to surgery. Non-anesthesia medical studies have indicated that inadequate patient-physician communication and an inadequate patient-physician relationship will result in misunderstanding and an increased malpractice risk. Lack of understanding of the duties and responsibilities of anesthesiologists is also damaging to the professional status of the field of anesthesiology. This study will utilize patient interviews and questionnaires to examine the degree of awareness that the patients and their families possess regarding what general anesthesia is, the duties and responsibilities of the anesthesiologist, the role of the anesthesiologist within the operating room and the specifics of what they are agreeing to by signing the consent form. If it is determined that a more structured and thorough pre-anesthesia discussion will help patients and their families understand what general anesthesia is, understand the specific responsibilities of anesthesiology providers, understand the professional status of anesthesiologists, give them a better feeling of autonomy and better understand what they are agreeing to by signing the consent form, then there will be substantial ramifications to the priority and importance given to pre-anesthesia discussions nationwide. Secondary benefits include influences on anesthesia residency training and malpractice actions against anesthesiologists. Improved patient satisfaction with the anesthesia experience is another potential secondary benefit.

### 2. Objectives (include all primary and secondary objectives)

Primary objectives: - Determine the percentage of people with an accurate knowledge of what general anesthesia is. - Define the public's perception of the role of the anesthesiologist in the operating room. - Help patients and the public to better understand the risks and safety aspects of anesthesiology Secondary objectives - Improve anesthesiologist-patient relations. - Decrease the likelihood of malpractice suits. - Improve the professional standing of anesthesiology. - Patients will know that the anesthesiologist is not a person who just puts them to sleep and then abandons them. - Decrease fear of the anesthesia experience. - Decrease fear of the anesthesia face-mask. - Improve medical student recruitment into anesthesiology as a career choice.

### 3. Background (briefly describe pre-clinical and clinical data, current experience with procedures, drug or device, and any other relevant information to justify the research)

The perioperative period can be fraught with a whole range of emotions from fear, depression and anxiety to calmness. The first patient encounter with his or her anesthesiologist most commonly occurs on the day of his or her procedure, and usually just a few hours before the procedure. This places an extraordinary responsibility in a

relatively short amount of time upon the anesthesiologist to engender confidence in his or her ability to provide the safest care for that patient. The more successful the anesthesiologist is in establishing a sense of professionalism and confidence, the more likely the patient will achieve satisfaction with the provider; the less successful the anesthesiologist, the less the patient's satisfaction. This has implications, if not for the direct outcome of the patient's procedure, certainly for the patient's perception of the success of the procedure's outcome.

Of note is that the journal *Current Opinion in Anaesthesiology* recently published an article titled "Communication between anaesthesiologists and patients: how are we doing it now and how can we improve?" [Curr Opin Anaesthesiol 22(3):431–435, 2009]. The article is a review on the subject of anesthesiologist–patient communication. In the results section of their article, the authors state, "Anaesthesiologists and patients may have different 'agendas' during their consultations, with anaesthesiologists focusing more on information and patients more on the emotional aspects of care. As effective communication implies a two-way process, anaesthesiologists should be aware of this." Within this article, the authors perceptively point out the lack of residency education regarding anesthesiologist–patient communication. "Many of the techniques used by experienced anaesthesiologists have not been formally taught to them, but have been learned instead as part of the informal or 'tacit' knowledge of anaesthetic practice." It is possible that issues related to the public's understanding of the anesthesia specialty and the professional standing of anesthesiology in the eyes of the public, other physicians, and other health care providers is partly a result of the specialty's failure to communicate effectively to the public. In the same way, the fact that a patient can have nine previous general anesthesia experiences but not really know what general anesthesia is or what the anesthesiologist was doing while he was asleep represents a communication failure on behalf of all of his previous anesthesia providers as well as the process with which we train anesthesia residents to communicate with patients. The authors of the above quoted *Opinions in Anaesthesiology* article state it well in their introduction, "Despite its importance in everyday practice, and its prescription as an essential part of postgraduate training in anaesthesiology in many countries, communication between anaesthesiologists and patients has been little studied."

#### 4. Study Procedures

- a. Study design, including the sequence and timing of study procedures (distinguish research procedures from those that are part of routine care).

Research Procedures will be integrated into the routine part of the preoperative pre-anesthesia session. .

A member of the study team will approach the anesthesiologists who will be in the control arm of the study. None of the study team members will be in a supervisory or evaluative role to the potential anesthesiologists to be approached. Patient participants will be approached and asked if they are interested in participating. Those who are interested and eligible will undergo the research informed consent process. Patients will be divided into a **control group** and an **intervention group**. Both groups will receive the above described post-operative questionnaires with the addition of selected questions regarding their prior experience with anesthesia, and their understanding of what the anesthesiologist is responsible for. During the post-operative questionnaire they will also be asked what percentage of the signed anesthesia consent they read and if they recall anything about it. The questionnaire will be completed postoperatively, over the phone or in person, no more than 3 days after the day of the procedure.

The **control group** will have their pre-op discussion performed by an anesthesiologist in a manner commensurate with their routine for preoperative discussion. These anesthesiologists are not part of the study team. These anesthesiologists will be approached by a member of the study team and asked for permission to participate and be observed; then their patients will also be approached for participation. These anesthesiologists will be audio-recorded. Remotely, a study team member will review the audio-recording and will use a check list to assess the content communicated during the preoperative discussion. The amount of time that the discussion takes will also be recorded.

The **intervention group** will have their pre-op discussion performed by one of the two study anesthesiologists who will perform their discussion with knowledge of specific material that must be addressed prior to completion of the discussion including:

1. Description of the type of anesthesia administered
2. Description of what that type of anesthesia is (eg. what is general anesthesia?)
3. The expected anesthesia related procedures to be performed and the possibility of additional procedures performed if necessary.
4. anesthesia risk
5. Intraoperative communication with the rest of the operating room team
6. Communication to the patient that everything done will be in the interest of safety
7. Plans for pain and nausea control
8. An offer to address any additional questions that the patient may have

These anesthesiologists will also be -audio-recorded. Remotely, a study team member will review the audio-recording and will use a check list to assess the content communicated during the preoperative discussion. The amount of time that the discussion takes will also be recorded.

A comparison of the questionnaire results between the control and intervention groups will be made, and data will be statistically analyzed at the end of the study and data entry period.

- b. If your study involves data/biospecimens from participants enrolled under other research studies with a written consent or under a waiver of consent, please list the IRB application numbers for those studies. Please note: Certificate of Confidentiality (CoC) protections applied to the data in source studies funded by NIH or CDC will extend to this new study if the funding was active in 2016. If this situation applies, Section 36, question 4 in the application will need to be answered “Yes” and “Hopkins Faculty” should be selected in question 7. No other documents are required. N/A
- c. Study duration and number of study visits required of research participants. Study duration is anticipated to be 6 months and does not require any follow up visits from the research participants.
- d. Blinding, including justification for blinding or not blinding the trial, if applicable. Patients will be blinded to the group that they are assigned to. (control vs. intervention).
- e. Justification of why participants will not receive routine care or will have current therapy stopped. This study does not interrupt routine care for patients.
- f. Justification for inclusion of a placebo or non-treatment group.  
A control group is used to show the standard without the intervention and will be used to compare any similarities or differences to outcomes in the intervention group. Having a **control group** eliminates the potential impact of all other variables.
- g. Definition of treatment failure or participant removal criteria.  
Failure of treatment could be failure to complete pre-anesthesia session; participants can be removed if it is later determined that the patient is not eligible; for example, if the patient ended up getting consented for spinal anesthesia instead of general anesthesia.
- h. Description of what happens to participants receiving therapy when study ends or if a participant’s participation in the study ends prematurely. When the study ends, it will not affect a participant’s routine care that is received outside the study. If a participant’s participation

ends prematurely, but after informed consent was obtained, then only the information obtained prior to the end of participation would be used as part of the study. If informed consent is not obtained, participant will not participate in the study. If research consent is obtained but surgery case is cancelled on the day of surgery, participant will be removed from study.

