**5. Inclusion/Exclusion Criteria**

Inclusion Criteria: Adult patients undergoing general anesthesia for elective cases

Exclusion Criteria: Patients under age 18; Patients not undergoing general anesthesia

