**7. Study Statistics**

- a. Primary outcome variable: Recall of risks, understanding of anesthetic plan
- b. Secondary outcome variables. Anxiety relief
- c. Statistical plan: Pearson's Chi-squared statistic for categorical variables and Mann-Whitney U Tests for scaled variables.
- d. Early stopping rules.  
Study may be stopped at any time if there is a medical or public health emergency.

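### Prior anesthesia experience is asked of every patient but given no stated role in the analysis, although the groups follow the provider and no randomization is described

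*Combined protocol and SAP*

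**What the plan says.** All references are to the combined protocol and SAP.

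- **Forming the groups (section 4a).** "Patients will be divided into a control group and an intervention group". No randomization, stratification or matching is described. Control patients are reached through non-study anesthesiologists who agree to take part; "then their patients will also be approached for participation". The intervention discussion is given by "one of the two study anesthesiologists".
- **Eligibility (section 5).** "Adult patients undergoing general anesthesia for elective cases". Anesthetic history is not restricted, so first-time and experienced patients both enter.
- **Data collected (section 4a).** Both groups receive the questionnaire "with the addition of selected questions regarding their prior experience with anesthesia, and their understanding of what the anesthesiologist is responsible for". Timing: "The questionnaire will be completed postoperatively, over the phone or in person, no more than 3 days after the day of the procedure". No measure of knowledge before the discussion is described.
- **Outcomes (sections 7a and 7b).** The primary outcome is recall of risks and understanding of the anesthetic plan. The secondary outcome is anxiety relief.
- **Analysis (section 7c).** The whole plan is "Pearson's Chi-squared statistic for categorical variables and Mann-Whitney U Tests for scaled variables".
- **Role of the control group (section 4f).** The plan states that having a control group takes away the influence of every other factor.
- **Experience and knowledge (section 3).** The background mentions "the fact that a patient can have nine previous general anesthesia experiences but not really know what general anesthesia is".

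**The concern.** The questionnaire measures what patients know after surgery, and there is no earlier measurement to compare it with. A patient who heard about anesthetic risks before a previous operation may name them without having learned them from this discussion. This applies more directly to risks, many of which are shared between procedures, than to the plan for the present procedure.

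That would matter little if the groups had similar histories. Nothing described in the plan secures this: group is tied to the anesthesiologist, and anesthesiologists may differ in the cases and patients they see. If the intervention group is the more experienced one, earlier learning can pass for an effect of the structured discussion. If it is the less experienced one, a real effect can be hidden. The plan collects an item that bears on this, but section 7c does not say how it will be used. Leaving the choice open also allows adjustment to be decided after the results are known.

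**Working it through.** **No figure to reproduce.** The documents give no sample size, significance level, power, response rate or allocation ratio. Everything below is an illustration under stated assumptions.

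**Assumptions.** Two-sided 5% test; 60% of controls have had prior anesthesia; 40% of patients without it answer an item correctly; 50, 100 or 200 patients per group. Two quantities are varied:
- g, the knowledge gap: chance of a correct answer with prior anesthesia minus the chance without;
- d, the imbalance: share with prior anesthesia in the intervention group minus the share in the control group.

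**Step 1: bias with no true effect.** Expected correct answers are 0.40 + 0.60g in controls and 0.40 + (0.60 + d)g in the intervention group. The spurious difference is therefore g × d.

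- Smallest case: 0.10 × 0.10 = 0.01, or 1 point.
- Middle case: 0.20 × 0.20 = 0.04, or 4 points.
- Largest case: 0.30 × 0.30 = 0.09, or 9 points (58% against 67%).
- No knowledge gap: 0 × d = 0 for any imbalance.

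**Step 2: false positives of the planned chi-squared test.** With p the mean of the two rates p₀ and p₁, and n per group, the test rejects when the difference exceeds 1.96·√(2p(1−p)/n). The actual standard error is √[(p₀(1−p₀) + p₁(1−p₁))/n]. For the largest case at n = 100, the threshold is 1.96 × √(0.625 × 0.375 × 2/100) = 0.134 and the standard error is √[(0.58 × 0.42 + 0.67 × 0.33)/100] = 0.068. Then (0.134 − 0.09)/0.068 is about 0.65, and the rejection probability is about 26%.

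| g | d | Spurious difference | n = 50 | n = 100 | n = 200 |
|---|---|---|---|---|---|
| 0 | 30 points | 0 points | 5% | 5% | 5% |
| 10 points | 10 points | 1 point | 5.1% | 5.2% | 5.5% |
| 20 points | 20 points | 4 points | 6.8% | 8.7% | 12.6% |
| 30 points | 20 points | 6 points | 9.4% | 14.0% | 23.3% |
| 30 points | 30 points | 9 points | 15.2% | 25.9% | 46.0% |

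**Step 3: masking.** With a true effect of +15 points and an intervention group 10 to 30 points less experienced, the expected difference is 15 points minus g × |d|. That is 15 − 1 = 14 points down to 15 − 9 = 6 points. At 100 per group, power falls from 57–61% with no imbalance to between 51% and 14%.

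**Step 4: stratified test.** A simulation of 20,000 runs per setting compared the planned test with a Cochran-Mantel-Haenszel test stratified by prior anesthesia.
- No true effect, (g, d) = (20, 20), (30, 20) and (30, 30) points: the stratified test rejected in 4.7% to 5.1% of runs at all three sizes. The unadjusted test rejected in 7.6% to 45.5%.
- True effect +15 points, g = 20, d = −20 points: power at 50, 100 and 200 per group was 20%, 36% and 59% unadjusted, and 32%, 57% and 86% stratified.
- True effect +15 points, g = 30, d = −30 points: 10%, 14% and 23% unadjusted, and 32%, 58% and 87% stratified.
- No knowledge gap, d = 30 points: both tests stayed near 5%.

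The simulation treats prior anesthesia as correctly reported and as the only difference between the groups. It shows what stratification does about this one factor and nothing more.

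**The case against.** **The knowledge gap may be small or absent.** A reader might infer that prior anesthesia is the chief source of what patients already know. No section says so, and the only relevant text, in section 3, points the other way: "the fact that a patient can have nine previous general anesthesia experiences but not really know what general anesthesia is". This stands, and it is why the range must include zero. It is, however, one illustration in the background, not evidence that experience and recall are unrelated.

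**The item may be compared after all.** Section 4a plans a comparison of questionnaire results between groups, and the prior-experience questions belong to that questionnaire. A descriptive comparison would fall within those words. The accurate statement is that no role in the analysis is specified, not that the item will be ignored.

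**The item could not have shaped the groups.** A reader might fault the plan for not balancing on it. As planned, the item is collected only after surgery, so it is not available when groups are formed. That charge is not made here.

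**The item is reported after the discussion.** The intervention explains what general anesthesia is, which could change how those patients classify their past anesthetics. Stratifying on a self-report of prior general anesthesia might then misclassify the two groups differently. This stands as a caution. The history itself is fixed before the discussion, and a plain question about any prior anesthesia is less open to reclassification.

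**The questionnaire wording is not in the documents.** Whether it supports a none/any split has to be confirmed.

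**Allocation is the larger problem.** If patients were randomized individually, the argument about systematic bias would largely fall away. If not, adjusting for one item leaves differences in provider, procedure and patients untouched. This stands and limits what the fix can claim.

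**Repeat enrollment.** Section 5 does not bar a patient from entering twice, but nothing indicates that this would happen often enough to matter. It adds no weight here.

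**Conclusion.** The point holds in a limited form. A plausible confounder of the primary outcome is collected in both groups and given no stated analytic role, in a comparison where group follows provider and randomization is not described. The unadjusted tests in section 7c therefore cannot support the statement in section 4f.

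The documents do not establish that a bias exists, how large it is or which way it runs. The 1 to 9 point range rests wholly on the assumed gaps and imbalances of 10 to 30 points, and the error rates also rest on the assumed group sizes, base rate and share of experienced controls. The change is still worth making: it is cheap, it protects in both directions, and in the no-gap simulation it left the false-positive rate near 5%.

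**What to change.** **Section 7c.** Add that prior anesthesia (none versus any) will be tabulated by group, and that the primary comparison will be stratified by it or adjusted for it. For categorical items, use the Cochran-Mantel-Haenszel test or a logistic regression with group and prior anesthesia, and name in advance which is primary. For scaled items, use the van Elteren stratified rank test in place of the plain Mann-Whitney test.

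**Questionnaire.** Confirm that the wording supports the none/any split. If it does not, ask one simple question on whether the patient has had any anesthesia before, without requiring the patient to identify the type.

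**Section 4f.** Withdraw or qualify the statement about the control group, and note that adjustment for this item does not remove other provider or patient differences. Section 4a should say how patients come to be in one group or the other.

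**Optional.** Results shown separately for first-time and experienced patients, and a line on repeat enrollment.

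**Cost.** A few lines of text. No new data are needed if the existing item supports the split; otherwise one reworded question. The remaining weakness is self-report after the discussion, which the simple wording reduces but does not remove.

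### Age, schooling and language are not named as collected or used, although recall is compared by unadjusted tests between groups with no described randomization

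*Combined protocol and SAP*

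**What the plan says.** **Outcome.** Section 7a gives the primary outcome as "Recall of risks, understanding of anesthetic plan". Section 4a has the questionnaire completed by phone or in person within 3 days of the procedure.

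**Allocation.** Section 4a says "Patients will be divided into a control group and an intervention group". No method, ratio or concealment is given. Section 4d speaks of patients being assigned, again without a method. Control patients are reached through non-study anesthesiologists, who are "asked for permission to participate and be observed; then their patients will also be approached for participation". Intervention patients "will have their pre-op discussion performed by one of the two study anesthesiologists".

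**Eligibility.** Section 5 admits "Adult patients undergoing general anesthesia for elective cases". There is no upper age limit and no language or literacy criterion.

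**Data named.** Both groups answer a core questionnaire plus "selected questions regarding their prior experience with anesthesia, and their understanding of what the anesthesiologist is responsible for". They are also asked how much of the consent form they read and what they recall of it. Discussions are audio-recorded, scored on a content checklist and timed. Age occurs only as the 18-year threshold in section 5. Schooling and language occur nowhere.

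**Analysis.** Section 7c reads, in full, "Pearson's Chi-squared statistic for categorical variables and Mann-Whitney U Tests for scaled variables". No covariates, stratification or baseline table are planned. Section 4f justifies the control arm on the ground that having one removes the influence of every other variable.

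**The concern.** How much of a spoken explanation a patient can repeat up to three days later plausibly depends on age, on schooling or health literacy, and on whether the conversation took place in the patient's own language. The plan admits the full adult range on all three.

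Randomization would make such traits balance in expectation, and an unadjusted test would be valid. Here none is described, and group is set by which anesthesiologist saw the patient. If the lists of the two study anesthesiologists differ in patient mix from those of the consenting control anesthesiologists, the difference passes directly into the comparison of recall. It can run either way, creating an apparent benefit or hiding a real one.

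The premise in section 4f does not help. A concurrent control group supplies a comparator; without randomization or adjustment it does not make the two groups alike.

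The gap may also be hard to repair afterwards. Section 8b removes identifiers at data entry, so a trait not recorded by then may not be recoverable by going back to the patient's record.

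**Working it through.** **No figure to reproduce.** The documents state no sample size, significance level, recall rate or effect size. Everything numerical below is an assumption, chosen to show the order of magnitude.

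**Set-up.** Treat recall as correct or incorrect. Divide patients into two strata, such as more and less schooled, with the same recall in each stratum whichever group the patient is in, so there is no true effect.

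Spurious difference = (recall gap between strata) × (difference between groups in the share of the better stratum).

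**Central example.** Assume recall of 65% in the more schooled and 35% in the less schooled, with 60% more schooled in one group and 40% in the other.

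- Group 1: 0.60 × 0.65 + 0.40 × 0.35 = 0.53
- Group 2: 0.40 × 0.65 + 0.60 × 0.35 = 0.47
- Spurious difference: 0.53 − 0.47 = 0.06, which equals 0.30 × 0.20

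**Rejection probability** of the two-sided 5% test of two proportions (equivalent to the uncorrected chi-squared test), with n per group:

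- SE under the null: SE0 = √(2 × 0.50 × 0.50 / n)
- SE at the actual rates: SE1 = √((0.53 × 0.47 + 0.47 × 0.53) / n)
- P(reject) = Φ((0.06 − 1.96 SE0)/SE1) + Φ((−0.06 − 1.96 SE0)/SE1)

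| n per group | SE0 | SE1 | P(reject) |
|---|---|---|---|
| 50 | 0.1000 | 0.0998 | 9.2% |
| 100 | 0.0707 | 0.0706 | 13.5% |
| 200 | 0.0500 | 0.0499 | 22.4% |

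**Range at 100 per group**, with strata and shares centred on 50%. Each cell gives the spurious difference and the false-positive rate:

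| Recall gap | Imbalance 10 points | Imbalance 20 points | Imbalance 30 points |
|---|---|---|---|
| 20 points | 2 points, 5.9% | 4 points, 8.7% | 6 points, 13.5% |
| 30 points | 3 points, 7.1% | 6 points, 13.5% | 9 points, 24.6% |
| 40 points | 4 points, 8.7% | 8 points, 20.4% | 12 points, 39.6% |

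**Below that range.** With recall of 50% against 60% and stratum shares of 50% against 60%, the spurious difference is 0.10 × 0.10 = 1 point, and the rate is 5.1% to 5.5% for 50 to 200 per group. With balanced groups it stays at 5%.

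The bias does not shrink as patients are added. Its standard error does, so a larger study is more likely to declare it significant.

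**The case against.** Four objections deserve weight.

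**The data may exist.** A reader might infer that age, schooling and language will not be collected, and that imbalance could be neither seen nor corrected. The documents do not support that. Section 4a refers to a questionnaire described above that is not itemized in the supplied text, and some pages were removed before review. Age has to be checked for every patient to apply section 5. Language and interpreter use would normally be audible on the recordings, though the plan does not say they are coded. Only schooling has no visible source. This objection stands, and it limits the point to what is named as collected and planned for use. It does not rescue the analysis: even if an item is in the questionnaire, section 7c makes no use of it.

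**The harm is conjectural.** Nothing in the documents shows that patient mix differs between anesthesiologists, or how strongly these traits affect recall. That is true. At the mild end the false-positive rate is close to nominal, and section 7a does not say that recall is scored as a binary outcome. The figures illustrate; they do not estimate.

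**The root problem is allocation.** Group is tied to provider, and three patient traits do not reach provider skill, clustering by provider, or how patients come to each provider. This stands as a limit on the remedy. It is not a reason to leave the traits unmeasured, because while allocation stays as described they are the least that is needed to see whether the groups are comparable.

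**Regression is one choice among several.** Stratification, or a baseline table with a sensitivity analysis, would also be defensible. With an unknown sample size and perhaps few interpreter-assisted patients, a model could be unstable. The fix allows for this.

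**Conclusion.** The point holds as a statement about what the plan names and intends. Recall and understanding are compared by unadjusted tests between groups that follow the anesthesiologist and have no described randomization. Of the patient background traits, only prior anesthesia experience is named as collected. No examination of, or correction for, imbalance in age, schooling or language is planned, and the statement in section 4f that would excuse this is not valid.

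The size cannot be derived from the documents. For a recall gap of 20 to 40 points and an imbalance of 10 to 30 points, with 100 per arm and no true effect, the spurious difference is 2 to 12 points and the false-positive rate is about 6% to 40%. These figures rest on assumed gaps, imbalances, numbers and binary scoring. Weaker confounding gives rates near 5%.

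This should be changed before enrolment. It is not evidence that the groups will in fact differ.

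**What to change.** 1. In section 4a, at research consent and before the discussion, record for both groups: age, highest schooling completed, and whether the discussion is in the patient's first language or through an interpreter.
2. Tabulate these by group.
3. In section 7c, make the primary comparison a regression of each primary element on group, age, schooling and language: logistic for a binary element, proportional-odds for an ordered one. Use few categories if numbers are small. Keep the chi-squared and Mann-Whitney results as unadjusted support.
4. Delete the sentence in section 4f that credits the control group with removing all other influences.
5. State in the plan that adjustment removes only measured patient-level imbalance and does not separate the intervention from the anesthesiologists who deliver it.

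**Cost.** Three short items per patient, one table, one model per primary element and a few degrees of freedom. The interpreter term may be unstable if interpreter use is rare. If patients were randomized instead, the table and covariates would remain useful but would no longer carry the comparison.

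### The consent-form items described capture reading and unscored recall, so on their own they cannot show better understanding of what was agreed to

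*Combined protocol and SAP*

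**What the plan says.** Section 1 (Abstract) says that interviews and questionnaires will examine, among other things, how aware patients are of "the specifics of what they are agreeing to by signing the consent form". It then lists the benefits that a more structured discussion might bring. One is that patients would "better understand what they are agreeing to by signing the consent form". That is a directional aim about comprehension.

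Section 4a (Study design) describes the instrument: "Both groups will receive the above described post-operative questionnaires with the addition of selected questions regarding their prior experience with anesthesia", and also questions on "their understanding of what the anesthesiologist is responsible for". On the consent form, it adds that "they will also be asked what percentage of the signed anesthesia consent they read and if they recall anything about it". The questionnaire is given once, within 3 days after the procedure. Section 4a closes by saying that questionnaire results will be compared between the control and intervention groups.

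Section 7 (Study Statistics) gives the primary outcome as "Recall of risks, understanding of anesthetic plan". The next entry is "Secondary outcome variables. Anxiety relief". The analysis uses Pearson's "Chi-squared statistic for categorical variables and Mann-Whitney U Tests for scaled variables". Neither Section 4 nor Section 7 gives a score, an answer key or a favourable direction for the two consent-form items.

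**The concern.** The aim is about understanding, but the consent-form items described are about reading and memory. A patient who reads 0% of the form after a full verbal explanation may understand all of it, and one who reads 100% may understand little. The recall item, as described, could be met by one minor or mistaken detail.

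Both items fall under the planned comparison of questionnaire results, so each can yield a p-value. A reader could take a difference in either direction as evidence about understanding of the consent, although neither item was built to carry that meaning. Section 1 attaches wide practical consequences to the benefits it lists, and this is one of them.

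Comprehension that is not measured at the single post-operative contact is unlikely to be recovered later, because Section 4c requires no follow-up visits.

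**Working it through.** The plan gives no figure for these items and there is nothing to recompute. The check sets the aim, the items and the analysis side by side.

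**1. Aim (Section 1).** Better understanding of what is agreed to by signing. More is better.

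**2. Items described (Section 4a) and test by variable type (Section 7).**

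| Item | What it captures | Favourable direction | Likely test | What a group difference would show |
|---|---|---|---|---|
| Percentage of form read | Self-reported exposure to the document | Unclear | Mann-Whitney U | Patients report reading more or less |
| Whether anything is recalled | Memory of unspecified content, with no stated check for correctness | More is plausibly better | Chi-squared, if recorded as yes/no (an assumption) | More or fewer patients report remembering something |

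Both tests can be run. Neither result would estimate understanding of the form.

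**3. Why percentage read has no clear direction.** Suppose the intervention works as intended. A patient who has had everything explained may see less need to read. A patient whose interest has been raised may read more. An effective discussion is therefore compatible with a fall, no change or a rise. None of the eight required discussion elements in Section 4a asks the anesthesiologist to go through the written form, so the intervention does not target reading directly.

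**4. Order of signing.** The plan does not say whether the form is signed before or after the discussion.
- If signed and read before, the discussion cannot change the percentage read before signing.
- If signed after, it can, but in the unclear direction of step 3.

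**5. What else might cover the aim.** The questions on the anesthesiologist's responsibilities concern a different subject, which Section 1 lists separately. The primary outcomes in Section 7 are closer, since risks and the anesthetic plan are part of what a patient consents to. Section 7 does not tie them to the signed form. The base questionnaire, to which the two items are additions, is not in the available text.

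**6. What depends on the two items.** Understanding of the consent form is not a listed objective in Section 2 or a listed outcome in Section 7. The listed primary and secondary comparisons therefore stand or fall without these items.

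**The case against.** The strongest reply is that the plan never calls percentage read or recall a measure of understanding. It says only that patients will be asked about them. They are supplementary questions, and treating percentage read as a descriptor is close to the status it already has. The base questionnaire cannot be seen, and Section 1 says the questionnaires will examine the point, so comprehension items may exist. The primary outcomes also overlap with much of what the suggested questions would ask. Finally, the protocol's account of the recall item is a description and not the questionnaire wording, which could be open-ended with the answers written down.

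Most of this stands, and it limits the point. A reader might infer that the plan defines consent-form understanding by these two items, or that the abstract's question cannot be answered at all. The documents support neither inference, for the reasons just given. A reader might also extend the unclear direction to both items. It applies only to percentage read; the weakness of the recall item is that it is crude and unscored. The yes/no format and the signing order are not stated, so no firm criticism can rest on either.

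What the reply does not remove is the gap in the text. The plan identifies no scored item on the content of the signed form, although Section 1 names that understanding as a benefit to be tested and Section 4a compares questionnaire results between groups.

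**Conclusion.** The point holds in limited form. The consent-form items that the plan describes measure reported reading and unspecified recall. On their own they cannot show that a structured discussion improves understanding of what was agreed to, whichever way the groups differ.

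The size cannot be quantified: the documents give no sample size, expected effect or scoring for these items, and the sign of any effect on percentage read is undetermined even if the intervention works. The consequence is confined to one aim in the abstract and leaves the listed primary and secondary comparisons untouched.

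The conclusion assumes that no scored consent-comprehension item exists in the base questionnaire. If one does, the remedy is to name it in the plan as the measure for this aim.

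**What to change.** Replace or supplement the recall item with three to five fixed factual questions on what the signed form authorizes, such as the type of anesthesia, possible additional procedures and named risks, where the form covers them. Use the same questions in both groups and score them from 0 to the number of items against a key written before data collection, with higher better. A score of this kind fits the Mann-Whitney test already planned.

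Report percentage read as a descriptor only, not as evidence of benefit, and record whether the form was signed before or after the discussion.

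If the questions are not added, and no existing questionnaire item covers the content of the form, limit any conclusion about the consent form to reading and recall.

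The cost is one or two more minutes per patient in a questionnaire already being given, plus a short answer key.
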